3.0 Study Design

This study will contain 2 cohorts, those with normal serum 25(OH)D and those with low serum 25(OH)D at enrollment. The study will take place in women with ovarian, primary peritoneal, and fallopian tube cancer, subsequently referred to as ovarian cancer in this document due to the overlap in disease and treatment.

Patients who have given written consent to enroll in the study will have a serum 25(OH)D drawn in a gold-topped tube (1 to 5mL volume) at time of enrollment and prior to initiation of treatment for their cancer. Serum 25(OH)D levels will be analyzed per laboratory protocol in our University CLIA certified lab. Blood will also be drawn for analysis of serum leptin levels and VDR *FokI* SNP genotype. A purple-topped tube (7 to 10mL volume) and red-topped tube will be collected from prospective patients. The Stephenson Cancer Center Biospecimen Bank will process the red and purple-topped tube into plasma and Buffycoats, label them with a de-identified code and transfer them to [name] lab. The plasma

will be used to evaluate leptin by ELISA and the Buffycoats used to evaluate the *FokI* SNP using PCR. Retrospective serum specimens will be used to measure leptin.

Patients with low serum vitamin D levels, defined as <20 ng/mL, will be provided a supply of cholecalciferol (vitamin D3), 50,000 IU weekly for 8 weeks that will be dispensed in the Stephenson Cancer Center outpatient pharmacy in order to standardize therapy. They will then be provided with a prescription for 2,000 IU of cholecalciferol (vitamin D3) daily following completion of 8 weeks of therapy based on current Endocrine Society guidelines in agreement with U.S. Preventive Services Task Force recommendations [14]. Treatment with cholecalciferol will not impact initiation of treatment for ovarian cancer. Compliance with cholecalciferol repletion will be assessed with medication reconciliation at every gynecologic oncology visit.

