Vitamin D therapy will be stopped in any patient developing the above exclusion criteria of GFR <30, inability to tolerate oral medications, malabsorption syndrome, or primary hyperparathyroidism. In the unlikely event of evidence of vitamin D toxicity, treatment with vitamin D will be stopped. The Stephenson Cancer Center laboratory defines vitamin D toxicity as levels >100 ng/mL. Based on IOM literature, it would highly unlikely for individuals to experience vitamin D toxicity at the prescribed doses. Symptoms of vitamin D intoxication are caused by the resultant hypercalcemia and include anorexia, weight loss, polyuria, arrhythmias, fatigue, and soft tissue calcifications [20]. Patients experiencing these symptoms would receive testing for serum calcium and vitamin D. Vitamin D treatment would be stopped for any value indicative of toxicity.

Demographic, clinical, and disease characteristics and outcomes will be collected from all patients prospectively. The patient's treatment course information will also be collected prospectively, but will not be dictated by this study. Serum 25(OH)D and leptin levels will be collected again at the completion of primary therapy, 6 months after the completion of primary therapy, and at the time of disease recurrence. If disease recurrence occurs prior to 6 months after completion of primary therapy, this time point will be omitted. If disease recurrence does not occur prior to 1 year, serum 25(OH)D and leptin levels will be drawn at the time of the 1-year surveillance visit. If patients remain vitamin D deficient at any of these follow-up time points, they will be referred to an endocrinologist or primary care physician for further work-up and treatment of their vitamin D deficiency. Patients who are vitamin D deficient at completion of therapy but were not previously on supplement will be

IRB NUMBER: 7488
IRB APPROVAL DATE: 11/23/2021

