referred to a primary care physician for further management. Data collection will continue for 1 year or until the time of disease recurrence. Patient's will no longer have data collected after obtaining serum 25(OH)D and leptin levels at the time of recurrence. A retrospective cohort of women with low serum 25(OH)D that did not receive repletion of vitamin D will be used as a control group for comparison. This control group will be identified from available tumor bank serum samples including those previously identified in the above-mentioned unpublished study at the University of Oklahoma. These samples will be used to evaluate serum levels of 25(OH)D, leptin, and evaluate Buffycots VDR SNP polymorphism for *FokI*.

Cohort	Therapy
1 (Normal 25(OH)D)	None
2 (Low 25(OH)D (<20ng/mL)	50,000 IU cholecalciferol weekly for 8 weeks followed by 2,000 IU daily thereafter

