9.0 Evaluation Criteria

9.1.1 Response Criteria

9.1.1.1 Evaluation of Biomarkers

Clinical Response

If serum 25(OH)D is initially below the lower normal limit, it must normalize ($>20\text{ng/mL}$) for a patient to be considered experiencing a complete response to repletion.

9.1.2 Progression-Free Survival:

Progression-Free Survival (PFS) is defined as the duration of time from start of treatment to time of progression or death, whichever occurs first.

9.1.3 Survival:

Survival is defined as the duration of time from start of treatment to time of death or the date of last contact.

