## 1. Objectives

### a. Primary Objectives

1. To assess the treatment-related morbidity (including 30-day postoperative surgical morbidity and chemotherapy-related morbidity) and 1-year disease-free survival in patients with deficient serum 25(OH)D levels at the time of ovarian, primary peritoneal, or fallopian tube cancer diagnosis who did and did not receive vitamin D repletion.

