#### **a. Eligible Patients**

1. The study population will consist of women with newly diagnosed ovarian, fallopian tube, or primary peritoneal cancer and no previous treatment.
2. A retrospective cohort of women with ovarian, fallopian tube, or primary peritoneal cancer and low serum 25(OH)D that did not receive repletion identified from available tumor bank serum samples.

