##### b. Study Drug Administration and Compliance

1. Pill counts at each patient visit will be utilized to document compliance with oral medication.

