#### 6. Antitumor Evaluation

1. Treatment related morbidity (including 30-day postoperative surgical morbidity and chemotherapy-related morbidity) will be summarized by descriptive statistics as appropriate and compared across groups (chi-square for categorical variable).
2. Progression-Free Survival (PFS) at end of study (EOS) is defined as the time in months from first dose of the drug to the date of death or the first documented date of progression, whichever comes first. For patients who did not die and did not have progression, the PFS is censored at the last documented tumor assessment.

Survival curve for PFS will be generated using the Kaplan-Meier method. Median PFS with 95% CI will be computed.

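### The SAP starts PFS at the first dose of vitamin D, a date the unrepleted controls do not have, and neither document defines the primary 1-year disease-free survival

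*SAP*

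**What the plan says.** The primary objective, worded alike in protocol 1.2.1 and SAP 1a, includes "1-year disease-free survival in patients with deficient serum 25(OH)D levels" and sets women who were repleted against women who were not. Neither document gives disease-free survival an event, a time origin or a censoring rule.

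The related endpoint that is defined is PFS, and it is defined twice:

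- SAP section 6, item 2: "time in months from first dose of the drug to the date of death or the first documented date of progression", censored at the last tumor assessment, with a Kaplan-Meier curve and a median with 95% CI.
- Protocol 9.1.2: "duration of time from start of treatment to time of progression or death, whichever occurs first".

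On the comparators, protocol 3.0 says: "A retrospective cohort of women with low serum 25(OH)D that did not receive repletion of vitamin D will be used as a control group". SAP 3a describes the same group as having "low serum 25(OH)D that did not receive repletion identified from available tumor bank serum samples". The cohort table in protocol 3.0 lists no therapy for women with normal 25(OH)D.

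For between-group analysis, SAP 2b plans a logistic regression of outcomes, repleted women against 75 controls, controlling for age, stage and histology. Protocol 12.0 repeats this and adds Kaplan-Meier and Cox regression for survival.

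**The concern.** A time-to-event comparison needs a time zero that can be found for every woman in it. The SAP's time zero is the first dose of an agent that defines one group and is absent by design from the other. An analyst who follows the text produces a PFS curve for repleted women and has nothing to set beside it. An analyst who wants a comparison must choose another origin, and the protocol's wording does not settle which. The controls are historical, and some come from an earlier institutional review, so their outcomes may already be known when that choice is made. The endpoint at stake is part of the primary objective, so the choice belongs in the plan.

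**Working it through.** **1. Which drug.** SAP 2a describes only cholecalciferol being dispensed. SAP section 4 defines the safety population by at least one dose of vitamin D. SAP 5b says: "Pill counts at each patient visit will be utilized to document compliance with oral medication". No other dosed agent is named in the SAP, so the drug in section 6 is cholecalciferol.

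**2. Who has a first-dose date.**

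| Group | First dose of cholecalciferol | Start of cancer treatment |
|---|---|---|
| Prospective, deficient, repleted | yes | yes |
| Retrospective, deficient, not repleted | none | yes, from records |
| Prospective, normal 25(OH)D | none by protocol | yes |

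**3. Share of the primary comparison without a time zero.** SAP 2b gives 75 controls and at least 25 repleted women. The share is 75/(75 + n), where n is the number repleted.

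- n = 25: 75/100 = 75.0%
- n = 30: 75/105 = 71.4%
- n = 40: 75/115 = 65.2%

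The values 30 and 40 are illustrations of the plan's phrase that at least 25 will be deficient.

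**4. Does protocol 9.1.2 repair it?** It does not say which treatment starts the clock. Protocol 3.0 uses the word for both within one sentence: "Treatment with cholecalciferol will not impact initiation of treatment for ovarian cancer". There are two readings:

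- Cancer treatment: every group has an origin, but it differs from the SAP's. Protocol 6.3 starts cholecalciferol when deficiency is diagnosed and does not tie it to the start of cancer care.
- Cholecalciferol: the two documents agree, and neither definition can be applied to the controls.

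Under both readings the SAP definition cannot be used for the controls.

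**5. Is the powered outcome touched?** The only power figure is 80% for chemotherapy delay, 33% against 65%, with 25 and 75 women. I assume two-sided alpha 0.05, which the documents do not state.

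- Pooled proportion: (25 × 0.33 + 75 × 0.65)/100 = 0.57
- Null SE: √[0.57 × 0.43 × (1/25 + 1/75)] = 0.1143
- Alternative SE: √[0.33 × 0.67/25 + 0.65 × 0.35/75] = 0.1090
- Power: Φ[(0.32 − 1.96 × 0.1143)/0.1090] = 0.811

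The stated 80% reproduces and does not depend on any PFS definition.

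**6. The year (secondary).** Protocol 3.0 schedules repeat samples "at the completion of primary therapy, 6 months after the completion of primary therapy, and at the time of disease recurrence", and a 1-year surveillance visit if there is no recurrence. The 6-month sample is tied to completion of therapy. Neither the 1-year visit nor the 1-year limit on data collection is tied to anything.

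To show the scale, assume a constant hazard, a share S of 60–80% event-free 12 months after treatment start, and T = 4–6 months of primary therapy. None of these is in the documents. Moving the assessment to 1 year after completion lowers the event-free share by S − S^((T+12)/12):

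| S | T = 4 | T = 6 |
|---|---|---|
| 0.6 | 9.4 points | 13.5 points |
| 0.7 | 7.8 points | 11.4 points |
| 0.8 | 5.7 points | 8.4 points |

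**The case against.** Four arguments on the other side deserve weight.

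*The documents need not conflict.* A reader might infer that the SAP flatly contradicts protocol 9.1.2. That holds only if the protocol means cancer treatment, which it does not say. The certain defect is narrower: the SAP's origin does not exist for the controls.

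*The plan does have a between-group route.* A reader might infer that the trial will yield no survival comparison at all. SAP 2b compares outcomes by logistic regression, and 1-year status is binary, so it could go there. Protocol 12.0 plans Cox regression, and nothing in the SAP withdraws it. This stands. What remains is that neither method is linked to disease-free survival, and both still need an origin. Nor is a Cox model adjusted for age, stage and histology already planned: protocol 12.0 attaches those covariates to the logistic regression. At the assumed 60–80% event-free, 100 women would give about 20–40 events, a thin basis for such a model.

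*The anchor leans one way.* The order of visits in protocol 8.1 and the word surveillance both suggest a year counted from completion of therapy, and those passages schedule blood draws and do not define the endpoint. This also stands, so the anchor is a secondary clarification.

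*A sensible analyst would use the start of cancer treatment.* Probably, but that is a choice the text does not make, for a primary endpoint with historical controls.

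**Conclusion.** The concern holds in this form: SAP section 6, item 2, cannot be applied to the unrepleted controls, who are 75 of 100 women in the primary comparison if exactly 25 are repleted. This rests on reading the drug as cholecalciferol, which the rest of the SAP supports. The missing definition of 1-year disease-free survival compounds it, because PFS is the only related endpoint with a stated definition.

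The 75% is the share of women without a time zero under one definition. It is not lost power or lost sample for the trial: the chemotherapy-delay calculation and the morbidity comparison in SAP section 6, item 1, are untouched. A reader might also take the 6–14 points in the working for bias. They are the spread in what the endpoint could mean, on assumptions from outside the documents, and they create no difference between groups that share one anchor.

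This should be fixed before outcomes are analysed. It does not call the design into question.

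**What to change.** 1. In SAP section 6, item 2, and protocol 9.1.2, use one origin that exists in every group, for example start of primary cancer treatment (first surgery or chemotherapy, whichever comes first).
2. State that 1-year disease-free survival is PFS at 1 year from that origin, or define it otherwise with its event, origin and censoring rule.
3. In SAP section 6, report the 1-year Kaplan-Meier estimate with 95% CI for the repleted and the unrepleted groups.
4. State which between-group analysis already planned applies to this endpoint: the SAP 2b logistic regression or the protocol 12.0 Cox model. If it is the logistic regression, say how women with unknown 1-year status are handled, since SAP section 9 rules out imputation.
5. As a secondary clarification, state what the year in protocol 3.0 and 8.1 is counted from, so that data collection reaches the endpoint.

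The cost is wording in both documents, plus abstraction of treatment-start and progression dates for the controls. If the year is counted from completion of therapy, completion dates for the controls are needed too, and prospective data collection must run to that point.

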12.0 Statistical Methods

Upon analysis, patients will be divided into two groups: Vitamin D Deficient Women and Vitamin D Normal Women.

IRB NUMBER: 7488
IRB APPROVAL DATE: 11/23/2021

Outcomes to be analyzed include differences in demographics, clinical, and tumor characteristics between groups, and differences in treatment-related morbidity or mortality between groups, including completion of treatment and treatment delays, and survival. Both 30-day postoperative surgical morbidity and chemotherapy-related morbidity will be assessed. The ability to normalize 25(OH)D levels with oral supplementation in the vitamin D deficient group will be evaluated.

Descriptive statistics will be used to summarize the demographic and clinical characteristics of patients. Chi-square and t-tests will be used to make comparisons between groups. Survival will be estimated with Kaplan-Meier curves and Cox proportional hazards regression. The anticipated enrollment is 100 patients based on estimated new diagnoses of ovarian cancer treated in the Division of Gynecologic Oncology annually at the Stephenson Cancer Center. Based on the previously mentioned unpublished data, we presume that at least 25 of the prospectively enrolled patients will be vitamin D deficient. All of the vitamin D deficient women will be repleted with oral vitamin D. We will compare outcomes between these patients and 75 vitamin D deficient ovarian cancer patients from previous years (these will include patients from the above-mentioned previous retrospective review as well as other patients with banked blood samples) using logistic regression. We will control for age, stage, and histology. With 25 prospective patients and 75 retrospective patients we will have 80% power to detect differences of 32% in chemotherapy delay between ovarian patients who were not vitamin D deficient (33%) and who were vitamin D deficient (65%).

Additionally, the association between serum leptin and 25(OH)D levels will be compared among groups, including any change in leptin levels observed in the vitamin D supplementation group. Because there is a positive linear association between BMI and serum leptin levels, BMI will be corrected for during analysis for potential relationships between serum leptin and 25(OH)D.

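### SAP section 6, item 2 plans a Kaplan-Meier curve and a median PFS, and no text assigns a method to the primary contrast of 1-year disease-free survival by repletion status

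*SAP*

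**What the plan says.** **Objective.** SAP section 1a and Protocol 1.2.1.1 make "1-year disease-free survival in patients with deficient serum 25(OH)D levels" part of the primary objective, comparing women who were repleted with women who were not.

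**Planned analysis.** SAP section 6, item 2: "Survival curve for PFS will be generated using the Kaplan-Meier method. Median PFS with 95% CI will be computed". Item 1 of that section compares morbidity across groups; item 2 says nothing about groups.

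**Endpoint definition.** Neither document defines DFS. The SAP has PFS, "defined as the time in months from first dose of the drug to the date of death or the first documented date of progression". Protocol 9.1.2 has PFS as the "duration of time from start of treatment to time of progression or death, whichever occurs first".

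**Follow-up.** Protocol 3.0: "Data collection will continue for 1 year or until the time of disease recurrence". Without recurrence, the last vitamin D and leptin "levels will be drawn at the time of the 1-year surveillance visit". The start of that year is not given.

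**Methods named elsewhere.** Protocol 12.0: "Survival will be estimated with Kaplan-Meier curves and Cox proportional hazards regression". That section opens by dividing patients into deficient and normal. Protocol 12.0 and SAP section 2b also plan a logistic regression of unspecified outcomes in 25 repleted and 75 unrepleted deficient women, controlling for age, stage and histology. The SAP does not mention Cox regression. SAP section 9 rules out imputation.

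**The concern.** One part of the primary objective is a proportion at a fixed time, compared between two groups. The only time-to-event analysis spelled out in the SAP is a curve and a median with no groups named. An analyst following section 6 would not produce the 12-month figure or the contrast. An analyst turning to section 2b could fit a logistic model to 1-year status, but would have no rule for women censored before 12 months. Two competent analysts could therefore report different primary survival results, or none.

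The median adds a second problem. It exists only if about half the women have an event within follow-up, and prospective follow-up is short. The controls come from earlier years and no truncation is stated for them. If medians were shown by group and control follow-up were longer, 'not reached' in repleted women could stand beside a numeric control median with no treatment effect behind it.

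**Working it through.** **1. The plan's own figure.** The only power statement concerns chemotherapy delay: 33% against 65%, 25 against 75 women, 80% power. Alpha is not stated; I take 0.05 two-sided.

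- Pooled rate: (25 × 0.33 + 75 × 0.65)/100 = 0.57
- Null SE: √[0.57 × 0.43 × (1/25 + 1/75)] = 0.1143
- Alternative SE: √[0.33 × 0.67/25 + 0.65 × 0.35/75] = 0.1090
- Power: Φ[(0.32 − 1.96 × 0.1143)/0.1090] = Φ(0.88) = 81%

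The stated 80% reproduces. It says nothing about DFS.

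**2. Does any text supply the missing method?**

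| Text | Groups | Method | Tied to 1-year DFS by repletion? |
|---|---|---|---|
| SAP 6, item 2 | none named | Kaplan-Meier curve, median | no |
| SAP 2b and Protocol 12.0 | repleted, unrepleted | adjusted logistic regression of outcomes | not named; no rule for censoring |
| Protocol 12.0, survival sentence | deficient and normal, as that section defines them | Kaplan-Meier, Cox | no |
| SAP 7 | three genotype groups | survival compared, method not named | no |

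**3. Chance that the median is reached, n = 25.** With no early censoring, the Kaplan-Meier curve falls to 0.5 or below once 13 of 25 women have had an event. So P(reached) = P(X ≥ 13), with X ~ Binomial(25, 1 − S(t)). The documents give no DFS rate, so S at 12 months is varied. The 16 and 18 month columns assume that the year starts after primary therapy, with exponential survival: S(t) = S(12)^(t/12). The total lengths are my assumption.

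| True 1-year DFS | 12 months | 16 months | 18 months |
|---|---|---|---|
| 40% | 85% | 99% | >99% |
| 50% | 50% | 85% | 93% |
| 60% | 15% | 48% | 64% |
| 70% | 2% | 11% | 19% |
| 80% | <0.1% | 0.4% | 1% |

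The planned 95% CI is harder to complete. On the log-log scale, a finite upper limit for the median needs 18 of 25 events. With 12 months of follow-up the chance of that is 15%, 2.2% and 0.1% at 1-year DFS of 40%, 50% and 60%.

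**4. Unequal follow-up, no treatment effect.** This illustration assumes the same exponential survival in both groups, 12 months for 25 repleted women and 24 months for 75 controls. P(not reached in repleted, reached in controls) = [1 − P(X ≥ 13 of 25)] × P(Y ≥ 38 of 75). At 1-year DFS of 60%, 24-month survival is 0.36 and the product is 0.846 × 0.993 = 84%. At 70%, 24-month survival is 0.49 and the product is 0.983 × 0.569 = 56%. Control follow-up is not stated in the documents.

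**5. What the right contrast would deliver.** With a common rate p, the 95% half-width for the 12-month difference is 1.96 × √[p(1 − p)(1/25 + 1/75)]: 22.6, 22.2, 20.7 and 18.1 points at p = 50%, 60%, 70% and 80%. Two-sided power for a 10-point gain from those control rates is 13% to 17%. For 80% power the gain must be about 31 points from 50%, 28.5 from 60% or 25.5 from 70%.

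**The case against.** The strongest reply is that the plan does compare these groups. SAP section 2b contrasts repleted and unrepleted deficient women with covariate adjustment, and 1-year DFS is a yes/no outcome that logistic regression could take if follow-up were complete. Protocol 12.0 adds Kaplan-Meier and Cox, and nothing withdraws them. This stands to the extent that a reader who infers that no comparison is planned goes too far. It does not close the gap. Section 2b never names DFS, logistic regression does not handle women censored before 12 months, and the protocol's survival sentence sits under a different pair of groups.

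The second reply is that a median can be perfectly estimable. A reader might infer that it usually is not, and the documents do not support that. They give no event rate. The order of the blood draws (end of primary therapy, 6 months later, then 1-year surveillance) is compatible with a year counted from the end of therapy. At 40% 1-year DFS the median is reached 85% of the time even with 12 months of follow-up. This reply stands.

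Third, 'not reached' is a legitimate result, and a 12-month value can be read off a Kaplan-Meier curve that extends to 12 months. That is true, but the SAP does not ask for that value by group or for a difference. The misleading pair of medians in step 4 also needs group-specific curves and longer control follow-up, neither of which is stated, so it is a risk and not a prediction.

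**Conclusion.** The point holds in this form: the time-to-event statistic in the SAP is not the primary endpoint, and no passage assigns a method to 1-year DFS by repletion status. That conclusion rests on the text alone and does not depend on any assumed rate or clock.

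Whether the median can be estimated does depend on assumptions. At 1-year DFS of 60%, the chance of reaching it in 25 women is 15% with 12 months of follow-up and 48% to 64% with 16 to 18 months. These figures assume no earlier censoring and, beyond 12 months, exponential survival. Even where the median is reached, it does not answer the stated objective.

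The time origin must be settled first. If the drug in the SAP's PFS definition means cholecalciferol, unrepleted controls have no time zero. The protocol's start of treatment can apply to both groups.

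**What to change.** In SAP section 6, item 2, replace the two sentences on the curve and median, and amend the origin, along these lines:

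- Define DFS (or state that PFS serves as DFS) and measure it in both groups from one origin that exists for both, such as start of cancer treatment, in line with Protocol 9.1.2.
- State when the 1 year of data collection starts, and check that it reaches 12 months from that origin. A year counted from an enrollment before treatment would stop short.
- Censor all women, including the banked controls, at 12 months from the origin.
- Report the Kaplan-Meier 12-month estimate with 95% CI in repleted and in unrepleted deficient women, and the difference with 95% CI.
- Report a Cox hazard ratio for repletion adjusted for age, stage and histology, the covariates already listed in SAP section 2b.
- Report a median only if it is reached in both groups within the 12 months.
- Say whether the logistic regression in section 2b applies to DFS. If it does, label it secondary and state how women censored before 12 months are treated.

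The cost is SAP wording and a few lines of code. No new type of data is needed, provided that progression dates and last assessments can be taken from the controls' charts. The downside is imprecision: a half-width of about 18 to 23 points under the assumed rates. The SAP should say that the 80% power refers to chemotherapy delay only and that the DFS contrast is to be read as an estimate with its interval.
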